SOCIAL PROTOCOL (HRP-580)**PROTOCOL TITLE: A Mobile Informatics Solution to Aid in Memory****VERSION DATE: 7/1/2022**

Principal Investigator/Faculty Advisor	Department: School of Public Health, Health Policy & Management [contact] Email Address: [contact]
Student Investigator	Name: N/A Current Academic Status (Student, Fellow, Resident): Department: Telephone Number: Institutional Email Address:
Scientific Assessment	I believe Scientific Assessment is not required.
Version Number/Date:	Version 19, date: 8/31/2023

SOCIAL PROTOCOL (HRP-580)

PROTOCOL TITLE: A Mobile Informatics Solution to Aid in Memory

VERSION DATE: 7/1/2022

REVISION HISTORY

Revision #	Version Date	Summary of Changes	Consent Change?
2	2	Phase 1 updates: Focus groups instead of interviews	Yes: phase 1 consent at focus group session instead of at time of screening and enrollment.
3	2/26/2020	Change in cognitive assessment tool and added details about phase 1 focus groups. Added context of care survey for care partners to complete.	Change in cognitive assessment tool
4	3/2/2020	1. Clarification provided on using Mini-Cog and UBACC in consent process. 2. Clarification on Baseline and 3 month survey	Clarification provided on using Mini-Cog and UBACC
5	5/6/2020	Focus Groups will now be conducted via Zoom meetings. If needed, dyadic interviews will also be conducted with participants in place of focus groups. Questions were added to phase I about changes in technology use due to the COVID-19 pandemic.	Yes: consent in phase 1 will now be conducted via Zoom, so consent will occur verbally with the caregiver and PWMC.
6	5/24/2020	No focus groups will be conducted, instead only dyadic interviews will be conducted. The SR Checklist survey will be administered verbally during the interview instead of after the interview via mail or web.	No
7	12/22/2020	Updating protocol and materials with new Primary Investigator (switched from [name] to [name]). Changes reflect that [name] was responsible for Phase 1 of the study while [name] is responsible for Phase 2 of the study.	No
8	3/28/2022	Updated to new protocol template version available from the UMN IRB. No changes were made to content of the protocol, unless it was not specified by the previous protocol.	No

SOCIAL PROTOCOL (HRP-580)

PROTOCOL TITLE: A Mobile Informatics Solution to Aid in Memory

VERSION DATE: 7/1/2022

9	5/25/2022	
Phase 1 specific content is colored green for ease of review (content was not changed since phase 1 has concluded).
 
Specific changes made to Phase 2 content: Updated staff changes, added brief pilot testing to ensure the study is not launched for multiple dyads before the technology has been debugged, added details about survey administration, added details about administering the UBACC before the follow-up surveys to ensure ongoing PWMC consent/assent, updated scales/information collected in the surveys, updated eligibility criteria so that the PWMC must live in the community, The TICS-40 will be administered to assess level of dementia severity and screen out participants who have severe dementia or no cognitive impairment, and added recruitment opportunities.
	
Yes: updated consent forms for CP and PWMC and a PWMC assent form; created CP and PWMC consent scripts for reviewing consent form over the phone; added details about administering the UBACC to PWMC prior to each survey to ensure ongoing consent or assent.

10	7/1/2022	
The survey has been broken into Care Person and PWMC surveys, and more specifically baseline and follow-up surveys have been created for each participant type to better assess the SR based on results from Phase 1. Additionally, the semi-structured interview, UBACC and email/telephone script have been revised for Phase 2. An infographic has been created to share phase 1 results with phase 1 participants. A screener form including the TICS-40 questions has been developed along with additional recruitment materials (emails, fliers, newspaper, and Facebook ads). Cover letters for email and mail communication have been created for Phase 2 as well as telephone scripts, for communicating with participants throughout the study duration. Details have been
	
Yes, the UBACC has been edited so that desired participant answers are updated for Phase 2. Additionally, consent processes are detailed further in the protocol.

SOCIAL PROTOCOL (HRP-580)

PROTOCOL TITLE: A Mobile Informatics Solution to Aid in Memory

VERSION DATE: 7/1/2022

		added about the RA's blinding to randomization and survey data collection procedures.	
11	9/2/2022	1) Updated the protocol's secure storage information (section 18) because the storage system intended for use has changed. 2) Also updated the protocol to reflect incentive payments of \$50 for 20 semi structured interviews. Previously, only the survey payments were listed. 3) Updated incentive payments to be paid via Visa Debit Cards instead of Greenphire ClinCards. 4) Uploaded updated consent forms and consent scripts to include semi structured interview payment and Visa card instead of ClinCard. 5) Uploaded updated cover letter templates to reflect semi structured interview and visa card payment were fitting. 6) Added [name], research assistant, and [name], research assistant, to the study.	Yes: updated consent forms and scripts to include \$50 participant payment if chosen for a semi structured interview and changed ClinCard to Visa card. Process of consenting remains the same.
12	11/10/2022	1) Updated the recruitment section of protocol (12) to include snowball recruitment and recruitment via professional network who works with target population. 2) Updated protocol to reflect reminder procedures for survey follow-up.	No.
13	12/13/2022	1)Specified the type of follow up surveys (Regular follow up, Bereavement or Long Term Care Transition), that would be administered to caregivers depending on their response to the disposition (section 5.2 note). 2)Specified the possibility of potential participants screening themselves out informally before completing a screener, due to the natural progression of conversation.	No.
14	1/25/2023	Edited inclusion criteria to remove criteria that they must remain in the	No.

SOCIAL PROTOCOL (HRP-580)

PROTOCOL TITLE: A Mobile Informatics Solution to Aid in Memory

VERSION DATE: 7/1/2022

		same area for next 6 months. Decided this is not required for the technology to work appropriately and may help with recruitment.	
15	2/14/2023	
1. Changed participant payment to Amazon gift card to allow for appropriately prorated amounts for those who do not complete all surveys, and to minimize fees that participants will face (as seen with Visa cards). Added further details about prorated amounts.
 
2. Updated Data Baking to allow for data sharing, which aligns with the grant and approved consent forms. This discrepancy was noticed in review of data sharing requirements.
	

LTFU	Lost to follow up

1.0 Objectives

1.1 Purpose:

We propose to develop an informatics system to assist people with memory impairment. Early stages of Alzheimer's and Alzheimer's related dementia often causes memory concerns. Persons with Memory Concern often cannot match names with faces or cannot recognize faces with a sure feeling of familiarity. Persons with Memory Concern (PWMC) may have difficulty remembering the names of family members and friends or may address them with a wrong name. They recognize the faces they see daily, such as a spouse or caregiver, but they may confuse visiting friends and grandchildren. The inability to remember names or relationships contributes to isolation and deeply affects their social lives. The proposed solution is a Smartwatch Reminder (SR) system to conspicuously provide this information to the PWMC when needed. This system will automatically transmit pictures and relevant information to a smartwatch worn by the PWMC when family or friends visit. The system will be evaluated on the target persons with memory concern population to measure engagement and improvements in social interactions and well-being.

Phase I Aims:

Aim 1: The phase I will develop a prototype SR system with limited features. It will work on one model of smartphone and smartwatch. The prototype system can be used to get feedback from potential users.

Aim 2: Examine the feasibility of the SR system for PWMC.

The result of Phase I will include user feedback that demonstrates the acceptability and perceived utility of the system.

Phase II Aims:

Aim 3: Phase II will develop smartphone and smartwatch apps designed to work with the popular products of 2022. The project will provide a smartwatch and tablet for dyads in the treatment group. Family, friends, etc. of the treatment group participants will be able to download a smartphone app from an online store. Instructional material will be created to show the suggested information that can be entered into the app.

Aim 4: Evaluate whether the Smartwatch Reminders exerts positive benefits for PWMCs' social engagement and well-being via an embedded experimental mixed methods design that combines the collection and analysis of qualitative data within a traditional randomized controlled trial (RCT) design.

2.0 Background

2.1 Significance of Research Question/Purpose: Millions of Americans have dementia, the loss of mental functions, e.g., thinking, memory, and reasoning, which interferes with

SOCIAL PROTOCOL (HRP-580)

PROTOCOL TITLE: A Mobile Informatics Solution to Aid in Memory

VERSION DATE: 7/1/2022

their daily functioning. While some cases of dementia are caused by medical conditions that can be treated, most cannot be reversed. Hence, the focus switches from treatment to palliative care, i.e., developing a plan to make life easier and more comfortable for individuals with dementia and their caregivers. The proposed project will develop an important tool to improve the well-being for persons with dementia. There are three types of strategies that have been utilized to assist people with memory problems: repetitive drill and practice, internal strategies for remembering, and external aids to cue or assist people with remembering(1). Only the third strategy, using an external tool, has been demonstrated to improve social interactions for patients with AD(1-4).

2.2 Preliminary Data: AME Corp. working with [name] at the University of Minnesota has recently completed a study of the use of a smartwatch to display the names of people in the vicinity that were identified by face recognition. AME called this system a Social Support Assistant (SSA). The SSA consisted of a smartwatch and a body worn device with a camera. The bodyworn device had a database of face images of the friends and family of the PWMC. Face recognition software in the bodyworn device matched the faces of people who approached the PWMC to the database. Each time a new face match occurred the picture and name would appear on the smartwatch. Other information could also appear to identify the relationship that person has with the PWMC. A phone app was developed that automated the creation of the face image database for the device worn by the PWMC's. This app allowed a new person to take selfies of their face at different angles to optimize the face recognition success. Another person could also use the app to take the pictures if the new person being enrolled could not do it themselves. The testing successfully showed that PWMC liked using reminders about friends and family.

2.3 Existing Literature: A recent review of intelligent assistive technology describes the products that have been or are under development for persons with dementia(5). It is significant that none of these devices has been tested in a clinical study with dementia subjects(5). There are also no electronic devices proposed to assist PWMC with the recognition of other persons. While little has been developed or tested for PWMC, electronic devices that store information and prompt users to attend to the information with alarm and messaging features have been tested with patients with memory impairments due to other neurological conditions with promising results(2). For all devices being developed for PWMC, it is important to consider their familiarity with the type of device prior to their disease due to their limited ability to learn new information(2). Aids that are simple to use and utilize familiar interfaces are most likely to be successful(2).

3.0 Study Endpoints/Events/Outcomes

3.1 Primary Endpoint/Event/Outcome:

Phase I: Twenty care partners will complete a system review checklist and context of care items in a dyadic interview setting. The intervention will be considered successful if at

SOCIAL PROTOCOL (HRP-580)

PROTOCOL TITLE: A Mobile Informatics Solution to Aid in Memory

VERSION DATE: 7/1/2022

least 75% of participants score an average of 4 (out of 5) points or higher on the checklist, indicating that SR met their needs (i.e., indicated agree or strongly agree that the SR was useful, acceptable, and feasible overall). This threshold has been used as a benchmark for success in prior research evaluating technological interventions for PWMC and their care partners(6-8). If the criteria for success are not met, the technology will be refined based on feedback and suggestions from PWMC and care partners, before conducting additional testing with the improved prototypes. Ample qualitative feedback will be available via the dyadic interviews to guide such refinement.

Phase II: Baseline and 6 month data will be used in a 2x2 repeated measures analysis of covariance to examine whether use of the SR results in statistically significant changes in PWMC negative health transitions and , social interaction, pleasant events, social stress, loneliness, relationship closeness, and community engagement and care partner well-being, such as social support, depression and burden (9). The primary independent variable in the proposed investigation consists of an indicator variable for random assignment into the SR treatment condition or the attention control group. Additional analyses will determine if covariates (context of care, mobile device proficiency, and dementia severity indicators) significantly vary across the SR treatment and attention control groups at baseline and over 6-months. If statistically significant variations between the SR treatment and control groups are found, baseline and/or change scores for these covariates will be included in all repeated measures analyses of covariance tests to provide additional statistical control.

3.2 Secondary Endpoint(s)/Event(s)/Outcome(s): We will apply a parallel convergent mixed methods design. Quantitative and qualitative data will be collected and analyzed separately, and then paired side-by-side for comparison(10, 11). Quantitative analyses are expected to provide breadth in presenting group-level trends, while qualitative analyses will provide insight into variation within these trends, and allow study participants to identify meaningful SR components for themselves. After independent quantitative and qualitative analyses, the results will be paired side by side for comparison. Researchers will identify and iteratively discuss areas of convergence and divergence to validate the results(10-13). The thematic codes and categories of implementation/use and mechanisms of benefit will be cross-tabulated with the empirical data from the randomized controlled evaluation to determine whether the findings diverge, converge, or highlight pathways toward additional questions and analysis(12, 13). This comparative, mixed method analysis approach may suggest how and why PWMCs experience the greatest benefit while using the SR.

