The RA will then ask the participants semi-structured questions to elicit open-ended data on the feasibility and utility of SR (see Appendix). The interview questions include prompts about technology more generally to elicit feedback about opportunities and barriers for technology to assist care partners and PWMC in navigating everyday life. This will provide a more comprehensive perspective regarding the feasibility and use of the SR system. Participants will provide in-depth information on the reasons why PWMC and care partners felt the SR will or will not be easy to use, and will point out barriers or facilitators to use that will be critical to address when refining SR prior to Phase II.

Phase I Data Collection.

18-item system review checklist. This will be completed verbally by care partners and PWMCs during the dyadic interviews. The checklist includes Likert items designed to measure both the PWMC and care partners' perceptions of the performance of SR in terms of ease of use, clarity, and quality of information provided.

Context of care. Questions will be completed verbally during the dyadic interviews. Care partners and PWMCs can complete the context of care variables. It includes items on geographic location, time since diagnosis, type of dementia diagnosis, Medicaid status, living arrangement of the PWMC, and demographics of the PWMC and the care partner.

Semi-structured questions. The RA will conduct dyadic interviews with Phase I participants to elicit open-ended data on the feasibility and utility of SR. Questions will also elicit feedback on how participants' technology use has changed due to the COVID-19

pandemic. The semi-structured questions will provide in-depth information on the reasons why PWMC and care partners felt the SR was or was not easy to use, and will point out barriers or facilitators to use that will be critical to address when refining SR prior to Phase II (33).

Phase II. Evaluate the Smartwatch Reminder Efficacy

Overview of Phase II. The primary goal of the SR is to facilitate social interaction for PWMC by providing facial recognition of family, friends, and other key people. In this Phase II study, the SR will be evaluated to determine whether it provides positive benefits for PWMC's social interactions and well-being.

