- Dementia severity. Care partners will complete validated measures of dementia severity including the PWMC's dependence on assistance with 6 activity of daily living tasks and dependence on assistance with 6 instrumental activity of daily living tasks(16-18, 50-52). An 8-item scale will assess the intensity of PWMCs' memory losses, communication deficits, and recognition failures at each time point (memory impairment)(19, 20). From the Dementia Severity Rating Scale, we are using one item about the PWMC's recognition of others (53). Additionally, during screening, the PWMC will complete the Telephone Interview for Cognitive Status (TICS-40) developed from the Aging, Demographics, and Memory Study), which will assess their level of dementia severity at the beginning of the study (50).
- Social interaction. Questionnaires will be administered to care partners to determine the frequency and quality of PWMCs' interaction in six different areas: in-person visits; telephone/video calls; traditional mail correspondence, text messaging, or email; and social media. Per the recommendations of prior research on informal long-term care, a prior week estimate will be completed that includes frequency and duration of each activity(22). A 7-day time-window was chosen as it is less prone to recall error. In addition to frequency data, satisfaction with the quality of interaction will be assessed on a simple 5-point scale, similar to prior reliable measures utilized in Alzheimer's disease and related dementias care partner intervention studies(23).
- Pleasant Events/Social Engagement. Care partners will complete the Pleasant Events Schedule-AD (PES-AD) Short Version (24, 25) for PWMCs. The PES-AD Short Version includes 20 items of events and activities for PWMCs. As originally constructed, the items of the PES-AD were within the capacity of individuals suffering from the earlier/milder stages of dementia, and thus were appropriate for inclusion in this Phase II project(24, 25). Items are rated according to their frequency during the past month and how much the PWMC enjoys the activity. An overall summary score assessing frequency of engagement in enjoyable activities is generated by multiplying each frequency and enjoyment item with each other and summing the resulting responses. The PES-AD has demonstrated excellent reliability and validity(24, 25).

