audit trail). In addition, patterns that link particular themes will be identified and discussed in successive meetings between [name] and [name] to identify more complex processes of Smartwatch use or this technology's pathways to benefit PWMC and their care partners. During monthly team meetings, the development of codes, categories, and themes will be reviewed with the other academic investigators (Drs. [name] and [name]) and the AME team to yield any additional input into these project components. The multiple team meetings and discussions will allow for an exploration of alternative interpretations of the qualitative data and will also provide a check regarding the quality and richness of the data collected during the embedded mixed methods components.

Phase II Quantitative Analysis: Data available at baseline and 6 months will allow for a 2x2 repeated measures analysis of covariance to examine whether use of the SR results in statistically significant changes in PWMC negative health transitions and , social interaction, pleasant events, social stress, loneliness, , relationship closeness, and community engagement and care partner well-being, such as social support, depression and burden (9). The primary independent variable in the proposed investigation consists of an indicator variable for random assignment into the SR treatment condition or the attention control group. IBM SPSS Statistics 21(41) will be used to conduct these analyses, as it supports a range of univariate, bivariate, and multivariate statistical analysis procedures. The team has extensive experience conducting longitudinal analyses on their prior research on dementia(5, 6, 42-44). Our proposed analyses will provide in-depth tests of the study hypotheses. Outcomes will include statistical significance of within-subjects, or 6-month change, in those in the Smartwatch Reminder treatment or control groups on key outcome variables (see above). Additional analyses will determine if covariates (context of care, mobile device proficiency, and dementia severity indicators) significantly vary across the SR treatment and attention control groups at baseline and over 6-months. If statistically significant variations between the SR treatment and control groups are found, baseline and/or change scores for these covariates will be included in all repeated measures analyses of covariance tests to provide additional statistical control.

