Phase II: A repeated measures analysis of covariance (ANCOVA) will be utilized to capitalize on the randomized design and the two sets of data that will be collected. The number of PWMC-care partner dyads to be enrolled to address study hypotheses was determined using power analysis procedures(45, 46). A sample size of 100 to identify a medium statistical effect (standardized regression coefficient = 0.15) at a suitable level of statistical power (0.80 is considered an excellent power value) is able to effectively incorporate up to 6 baseline covariates that vary significantly across the randomly assigned Smartwatch Reminder treatment and control conditions if they exist (as random assignment is often used to ensure statistically comparable treatment and control conditions, we feel this is a conservative estimate of baseline covariates)(46). Specifically, we relied on statistical power tables by the expert statistician Cohen(46) to conduct our assessment of power. As noted in Table 2 of Cohen (1992)(45), an alpha level of .05, a medium effect size of .15 (as opposed to using specific measures, Cohen operationalized a medium effect size of .15 as one that is observable, and a survey across the social sciences suggested that this proposed effect size was close to the average of observed effects), and a multiple regression model (similar to an ANCOVA) that includes up to 6 covariates requires a sample size of 97. For these reasons, an expected sample size of 100 PWMC and care partner dyads will be sufficient to conduct the Phase II efficacy evaluation. We anticipate having less than a 3% attrition rate which will ensure we maintain sufficient power. As noted in various recommendations for mixed methods sampling, 20 participants is considered an adequate sample size for semi-structured interview protocols to ensure the richness and depth of open-ended data collected(36, 47).

17.3 Statistical Analysis:

Statistical analyses used will include calculation of frequencies, bivariate correlations, t-tests, chi-square tests, and repeated measures ANCOVA as detailed above.

17.3 Data Integrity:

SOCIAL PROTOCOL (HRP-580)

PROTOCOL TITLE: A Mobile Informatics Solution to Aid in Memory

VERSION DATE: 7/1/2022

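### Phase II puts eight to ten or more unranked outcomes under Primary with no multiplicity rule, and never names the model term that decides efficacy

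*Combined protocol and SAP*

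**What the plan says.** Section 3.1 (Primary) gives the Phase II outcomes in one sentence: negative health transitions of the person with memory concerns (PWMC), then "social interaction, pleasant events, social stress, loneliness, relationship closeness, and community engagement and care partner well-being, such as social support, depression and burden". Section 17.1 repeats the list. The analysis is a 2x2 repeated measures analysis of covariance on baseline and 6-month data. On the treatment effect, 3.1 adds: "The primary independent variable in the proposed investigation consists of an indicator variable for random assignment into the SR treatment condition".

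Section 3.2 (Secondary) opens with "We will apply a parallel convergent mixed methods design" and contains only the comparison of quantitative with qualitative findings.

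Section 17.1 describes the result to be reported as follows: "Outcomes will include statistical significance of within-subjects, or 6-month change, in those in the Smartwatch Reminder treatment or control groups on key outcome variables".

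Section 17.2 gives the only alpha in the plan, "an alpha level of .05, a medium effect size of .15", for one regression model with up to six covariates. It concludes that 100 dyads "will be sufficient to conduct the Phase II efficacy evaluation". The list of methods in 17.3 includes no multiplicity procedure.

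The Phase II overview in Section 5.2 says: "The primary goal of the SR is to facilitate social interaction for PWMC". For that outcome, the data collection text says "a prior week estimate will be completed that includes frequency and duration of each activity", together with a 5-point satisfaction rating, over several kinds of contact.

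**The concern.** A trial described as an efficacy evaluation should state which result decides it. Here every outcome has the same standing, so the plan does not exclude claiming efficacy on whichever one reaches significance. It states no such rule, but it states no other rule for Phase II either, whereas 3.1 does give Phase I an explicit success threshold.

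The number of tests is also open:

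- Care partner well-being is introduced by examples. Section 5.2 adds an identity scale under that heading and gives the social network scale to both members of the dyad.
- The Phase II measures in 5.2 name no scale for social stress.
- Negative health transitions has no stated source. The disposition survey or the global health scale may be meant.
- Social interaction yields frequency, duration and satisfaction by type of contact, with no stated way to reduce them to one score.

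The second gap is the deciding term. The 2x2 model and the treatment indicator imply a group-by-time test, but neither 3.1 nor 17.1 says so. The 17.1 sentence on within-subjects change can mean group-by-time, a separate test in each arm, or the overall time factor. Only the first is a treatment effect. In a progressive condition both arms may change over six months whether or not the system works.

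**Working it through.** **1. The plan's own figure.** Section 17.2 states N = 97 for alpha 0.05, power 0.80, effect 0.15 and six covariates. This was checked as an omnibus F test with u = 6 and v = N − 7 degrees of freedom, noncentrality 0.15 × N, taking 0.15 as f². Power is 0.798 at N = 97, 0.803 at N = 98 and 0.813 at N = 100. The figure reproduces to within one dyad. It refers to one model for one outcome at 0.05, so it makes no allowance for eight to ten outcomes, and as an omnibus test it does not single out the treatment term.

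**2. The count.** There are seven PWMC outcomes: negative health transitions, social interaction, pleasant events, social stress, loneliness, relationship closeness and community engagement. Care partner well-being counts as one domain (7 + 1 = 8) or as its three named examples (7 + 3 = 10). Twelve is an illustration, not a stated list. It takes one score each for social interaction, pleasant events, loneliness, social network (PWMC), social network (care partner), socioemotional support, relationship closeness, community engagement, depression, burden, identity and global health.

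**3. Chance of at least one false positive.** Assumptions: between-arm tests, each at two-sided 0.05, no true effect on any outcome. Independent outcomes: 1 − 0.95^8 = 0.337 and 1 − 0.95^10 = 0.401. For correlated outcomes, take standard normal statistics with common correlation ρ and integrate over the shared factor u:

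P = 1 − ∫ φ(u) [Φ((1.96 − √ρ·u)/√(1−ρ)) − Φ((−1.96 − √ρ·u)/√(1−ρ))]^k du.

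For false positives favouring the system, the second Φ term is dropped.

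| Outcomes k | Direction | ρ = 0 | ρ = 0.3 | ρ = 0.5 | ρ = 0.7 | Single test |
|---|---|---|---|---|---|---|
| 8 | either | 33.7% | 30.0% | 25.0% | 19.1% | 5% |
| 10 | either | 40.1% | 35.1% | 28.7% | 21.3% | 5% |
| 12 (illustration) | either | 46.0% | 39.7% | 31.9% | 23.2% | 5% |
| 8 | favours system | 18.3% | 15.2% | 12.5% | 9.5% | 2.5% |
| 10 | favours system | 22.4% | 17.8% | 14.4% | 10.7% | 2.5% |
| 12 (illustration) | favours system | 26.2% | 20.2% | 16.0% | 11.6% | 2.5% |

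The documents give no outcome correlations. Several outcomes are reported by the same care partner, so the correlated columns are the more realistic ones.

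**4. The within-arm reading.** Suppose both arms have the same true change and each arm's own test is significant with probability p. The pattern of significance in the system arm but not in control then has probability p(1 − p). With no change, p = 0.05 gives 0.05 × 0.95 = 0.0475, about 4.8%. With 50% power in each arm it is 0.5 × 0.5 = 25%. That pattern is not a treatment comparison.

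**5. The remedy.** With one primary test at 0.05, and Holm on the rest only if it is significant, no claim is possible without a significant primary test, so the overall error under no effect is 5% at any correlation. A simulation of 400,000 trials gave 0.050. If the primary effect is real with 80% power and the other outcomes are null, a false secondary claim occurs in 1.6 to 3.9% of trials (seven or nine secondaries). Without the gate, a primary test at 0.05 plus a separate Holm family at 0.05 gives 9.6% if independent and 9.0%, 8.0% and 6.7% at ρ = 0.3, 0.5 and 0.7 with seven secondaries (nearly the same with nine). The gate is therefore needed to hold 5%.

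**The case against.** The strongest reply is that the error rates rest on a rule the plan does not contain. It nowhere says that each outcome is tested at 0.05, nor that one significant result is enough. That is correct, and the percentages are conditional on both. But the plan gives one alpha, no adjustment and no other rule for Phase II, so nothing in it prevents that reading.

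Second, a 2x2 model with the randomization indicator as the main independent variable points to group-by-time, which is itself a within-subjects effect in that model. This has force: on this half the defect is one of wording. It still needs correcting, because the 17.1 sentence permits within-arm tests.

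Third, the surveys are in an Appendix that is not in the supplied text, and it may identify the social stress measure. Section 5.2 also says that mean and sum scores will be calculated for all scales. The first point limits what can be said about social stress. The second does not yield one social interaction score across frequency, duration and satisfaction.

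Fourth, social interaction is named as the goal of the device, while Aim 4 speaks of social engagement and well-being, and the pleasant events scale already has a defined summary score. That is a fair reason to leave the choice to the investigators.

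Last, this is a minimal-risk behavioural study of 100 dyads, and labelling the outcomes exploratory would largely resolve the point. It would, but the plan presently calls Phase II an efficacy evaluation.

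**Conclusion.** The concern holds and should be corrected before outcomes are seen by arm. Nothing in the plan says which result decides Phase II or holds the error rate at 5%. If any one of eight to ten outcomes may carry the claim, the false-positive chance is 19 to 35% at correlations 0.7 to 0.3 and 34 to 40% under independence. In favour of the system it is 10 to 18% and 18 to 22%, against 2.5%. Even the mildest case, eight outcomes at correlation 0.7, is nearly four times the nominal 5%. These figures rest on assumed correlations, two-sided tests at 0.05 and no effect on any outcome. The absence of a ranking, a multiplicity rule and a named deciding term is read directly from Sections 3.1, 3.2 and 17.1 to 17.3 and depends on none of those assumptions.

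**What to change.** Amend Sections 3.1 and 17.1, with a dated record that the choices were made before any look at outcomes by arm:

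1. Designate one already-collected outcome as primary and give the reason. Social interaction is the natural candidate given the stated goal of the system, but the choice belongs to the investigators. If it is chosen, define one summary score from the frequency, duration and satisfaction items.
2. Name one primary test of system against control at two-sided 0.05: the group-by-time term of the planned 2x2 model. A 6-month between-arm difference adjusted for baseline would also serve, but only one of the two may be named.
3. List every other outcome by instrument and respondent. Make each either secondary, tested with Holm only if the primary test is significant, or exploratory, with confidence intervals and no efficacy claim.
4. Reword the 17.1 sentence on within-subjects change so that the between-arm difference in 6-month change is the test and change within each arm is descriptive only.

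The cost is the rewording and the dated record. No new data are needed, and one primary test at 0.05 requires no split of alpha. The downside is that the other outcomes can no longer support an unadjusted efficacy claim, and under the gate they support none if the primary test is not significant.
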